## 9 STATISTICAL CONSIDERATIONS

## 9.1 STATISTICAL HYPOTHESES

Primary Endpoint: We hypothesize that at least 60% of eligible patients approached will enroll in the Pathways intervention in the Phase II feasibility study.

## 9.2 SAMPLE SIZE DETERMINATION

The target sample of 6 patients for Phase I is based on the aim of refining procedures and content. We anticipate that 6 will be sufficient given that we have already had patients review proposed intervention materials to provide feedback and initial refinement.

The target sample size of 40 evaluable cases for Phase II is based on the goal of estimating the probabilities and means for 3 feasibility outcome measures (enrollment  $\geq$  60% [primary], retention  $\geq$  70%, adherence [defined as completing at least 3/5 sessions]  $\geq$  70%). We will use feasibility outcomes to inform an efficacy trial. Here we present some basic power calculations for the above 3 outcomes. Assuming a negative binomial distribution and true probability of enrollment of 60%, the probability that we would have to approach 55 or more people to recruit 40 is  $<0.05$ . If we approach  $\geq$  55 patients to enroll 40, it is unlikely the true probability of enrollment is 60% or greater, concluding a future efficacy study with our criteria may not be feasible. Out of 40 patients, if the true probability of retention is 60% we expect at least 19 patients will be retained (i.e., probability of  $n \leq 19$  retained given true retention probability of 60% is  $<0.05$ ), so if more than 21 patients are not retained, an efficacy study may not be feasible. We have 80% power (using a 2-tailed alpha of 0.05) to detect an adherence proportion of 0.72 if we assume a null hypothesis adherence proportion of 0.50.

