## 5.4 STRATEGIES FOR RECRUITMENT AND RETENTION, PARTICIPANT COMPENSATION

### **Recruitment and Enrollment.**

*Feasibility of Recruitment.* The Markey Cancer Center sees 294 newly diagnosed advanced stage lung cancer patients a year. We estimate 80% will meet performance status and brain

metastases criteria, 85% will receive required active oncologic treatments, and 10% will be excluded for already accessing palliative care or actively receiving psychological services. We estimate 179 patients per year will meet eligibility criteria. With a 50% recruitment rate (based on current estimates during COVID-19), we project recruiting 6 patients in 2 months (Phase I) and 55 patients (Phase II) in 8-9 months.

**Recruitment Strategies.** As in prior work, we will use two primary recruitment strategies: direct patient referral from oncologists and providers at the Markey Cancer Center and review of patient (per report of patients coming to clinic with diagnostic codes for metastatic lung cancer) and provider appointment schedules at the MCC. To facilitate pre-screening for eligibility, we will use the UK CCTS to have an honest broker build a report in Tableau of patients with upcoming Markey Cancer Center appointments and diagnostic codes for metastatic lung cancer. Tableau will link the CCTS Enterprise Data Warehouse data for this information and generate a report that the study team can access via a dashboard in Tableau. Tableau is a secure system that requires SSL and linkblue authentication. Additional eligibility checks may need to occur from within the UKHC medical record. Study personnel will identify upcoming oncology appointments of patients pre-screened for eligibility. Study personnel will then recruit patients in person at clinic appointments or by telephone.

We are requesting a waiver of HIPAA authorization for recruitment purposes. This waiver will allow us to review appointment schedules at the MCC to pre-screen potential patients for eligibility through the electronic health record. Patients will be pre-screened for documentation in their EHR for inclusion and exclusion criteria.

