## 9.4 STATISTICAL ANALYSES

### 9.4.1 GENERAL APPROACH

For Phase I we will use qualitative methods to analyze patient feedback from the exit interviews and descriptive statistics to summarize participants' acceptability ratings of the intervention. The interviews will be transcribed verbatim and managed in ATLAS.ti or other qualitative software for analysis. The PI and study coordinator will code interviews by domains (e.g., session relevance, delivery mode, ease of participation). Data will be analyzed using thematic content analysis to describe patient perceptions and identify patterns in the patient experience. Quantitative and qualitative findings from Phase I will be synthesized along with interventionist process notes and

included in a report. This report will be used to determine potential refinement in the recruitment procedures, intervention content, intervention delivery, fidelity forms, and retention strategies. The study team will review this report to reach consensus on refinements needed for Phase II testing.

For Phase II, we will use descriptive statistics (means, standard deviations, median, range) to examine the distribution of continuous variables. We will calculate 95% CIs for each of the feasibility measures to determine the range of estimates that are consistent with our data.

We will use one-sample negative binomial probabilities and tests of binomial proportions to compare rates of feasibility to hypothesized values. We will also summarize reasons for patient ineligibility and refusal to participate. In exploratory analyses, we will monitor and compare the patients who drop out or do not complete 3 or more sessions by demographic and clinical characteristics, and baseline scores of the measures (e.g., distress, lung cancer stigma). We will also investigate any differences in patient enrollment, retention, or adherence by treatment type (chemotherapy vs. immunotherapy) to identify an optimal patient population for a future study.

We will calculate inter-rater reliability for fidelity scores between raters of intervention fidelity.

Statistical significance will be indicated by  $p < .05$ .

---

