#### 9.4.2 ANALYSIS OF THE PRIMARY ENDPOINT(S)

The primary outcome of the feasibility is enrollment ( $\geq 60\%$ ). A one-sample binomial test will be used to compare the observed enrollment percentage to 60%.

Enrollment (primary): Number of patients enrolled divided by the number of eligible patients approached

Retention: The percentage of patients who complete baseline and post-treatment questionnaires

Adherence: The percentage of patients who complete at least 3 of 5 sessions in 10 weeks.

Acceptability: Mean post-treatment patient ratings  $\geq 7/10$  on intervention satisfaction (primary), convenience, helpfulness, relevance, recommendation to others, worth doing (0 = not at all to 10 = extremely); and a brief semi-structured interview to explore factors associated with acceptability

---

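### Section 9.2 misstates the enrollment probability: at a true 60% rate, approaching 55 or more patients to recruit 40 has probability 0.978, not below 0.05

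*Combined protocol and SAP*

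**What the plan says.** The primary hypothesis in Section 9.1 is that "at least 60% of eligible patients approached will enroll in the Pathways intervention" in Phase II. Section 9.4.2 and the separate Analysis Plan define enrollment as patients enrolled over eligible patients approached, and both specify the analysis: "A one-sample binomial test will be used to compare the observed enrollment percentage to 60" percent. Section 9.4.1 and the Analysis Plan also announce a second tool: "We will use one-sample negative binomial probabilities and tests of binomial proportions to compare rates of feasibility to hypothesized values".

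The only operating characteristic for enrollment is in Section 9.2. It starts from "The target sample size of 40 evaluable cases for Phase II". Then, "Assuming a negative binomial distribution and true probability of enrollment of 60" percent, it states that "the probability that we would have to approach 55 or more people to recruit 40 is" less than 0.05. For any count of 55 or higher it draws this conclusion: "it is unlikely the true probability of enrollment is 60% or greater, concluding a future efficacy study with our criteria may not be feasible".

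Section 5.4 plans recruitment on a lower figure: "With a 50% recruitment rate (based on current estimates during COVID-19"). Section 9.3 gives the Phase II sample as 55, not 40.

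**The concern.** The stated probability fails a simple check. If 60% of those approached enroll, 40 enrollments need about 67 approaches on average, so needing at least 55 cannot be rare. The inference drawn from it then points the wrong way near the limit: 40 enrolled out of 55 is 72.7%, well above the target, but Section 9.2 treats it as a warning.

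Enrollment is the primary endpoint, and Section 9.2 says the feasibility outcomes will inform an efficacy trial. The documents plan negative binomial probabilities as part of the analysis, and 55 is the only limit they give for that purpose. A team applying it as printed would probably question feasibility after a result that meets the protocol's criterion.

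**Working it through.** **Inputs.** True enrollment probability p = 0.60, target r = 40 recruited, limit 55 approached and stated probability below 0.05 (all Section 9.2). Feasibility criterion of at least 60% (Sections 9.1 and 9.4.2). Phase II enrollment of 55 (Section 9.3).

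**Formula.** Let N be the number approached when the r-th patient enrolls. N is at least n exactly when the first n − 1 approached yield at most r − 1 enrollments, so

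P(N ≥ n) = P(Bin(n − 1, p) ≤ r − 1).

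**The plan's figure.** P(N ≥ 55) = P(Bin(54, 0.6) ≤ 39) = **0.978**. As a rough check, Bin(54, 0.6) has mean 32.4 and SD √(54 × 0.6 × 0.4) = 3.6, so 39 lies nearly 2 SD above the mean. On the scale of N, the mean is 40/0.6 = 66.7 and the SD is √(40 × 0.4)/0.6 = 6.7.

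**Other readings.** None makes the sentence true as written.
- More than 55 approached: 0.965.
- 55 or fewer approached (the opposite tail): 0.035.
- 55 taken as refusals, so 95 or more approached: 0.0002. This is below 0.05 but is not what the sentence describes.
- A smaller target with the same limit: 0.029 for 26 recruited, 0.052 for 27.
- The true rate at which P(N ≥ 55) equals 0.05 for 40 recruited: 82%.

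A reversed tail or a limit left over from a smaller target could each explain the figure. The amendment log records a rise to 40 without giving the earlier number, so the documents do not settle which.

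**How the printed limit behaves (40 enrolled).** For N = 55 to 66 the observed rate runs from 40/55 = 72.7% to 40/66 = 60.6%, so the criterion is met. At N = 67 it is 59.7%.

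| True rate | Flagged: P(N ≥ 55) | Flagged although observed rate ≥ 60%: P(55 ≤ N ≤ 66) |
|---|---|---|
| 50% | 0.9997 | 0.05 |
| 60% | 0.98 | 0.49 |
| 65% | 0.90 | 0.71 |
| 70% | 0.69 | 0.65 |
| 75% | 0.37 | 0.36 |
| 80% | 0.11 | 0.11 |

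**Against the Section 9.4.2 test.** At 40 of 55, the exact one-sided p-value for a rate below 60% is 0.98. At 40 of 60 (66.7%), the criterion is met, Section 9.2 flags the result, and the exact test is inconclusive (two-sided p = 0.36, 95% CI 53% to 78%).

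**Limits that do give a probability below 0.05 at a true 60% rate.**

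| Enrolled | Limit approached | P at limit | P one lower | Observed rate at limit | Exact test against 60%: two-sided / one-sided p | Exact 95% CI | P(flag) at true 50% |
|---|---|---|---|---|---|---|---|
| 40 | 79 | 0.047 | 0.061 | 50.6% | 0.107 / 0.058 | 39% to 62% | 0.55 |
| 55 | 106 | 0.046 | 0.058 | 51.9% | 0.092 / 0.055 | 42% to 62% | 0.65 |

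**The case against.** The strongest reply is that little depends on the sentence. It is offered among basic power calculations for a single-arm pilot whose aim is estimation, and its conclusion is hedged. The primary analysis is the observed proportion with a binomial test and a 95% confidence interval; none of these uses 55, and the separate Analysis Plan omits the limit. All of this stands and bounds the consequence. It does not make the stated probability right, and no text says that Section 9.4.2 takes precedence over the reading in Section 9.2.

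Three narrower points also have some force.
- The limit does discriminate, but around the wrong rate: the flag probability falls from 0.98 at 60% to 0.11 at 80%. At 50% and 60% it is close to 1, so it cannot tell those two apart. Likewise, the inference against 60% is unsupported for 55 to 78 approached but does hold, by Section 9.2's own standard, from 79 upward.
- The 50% in Section 5.4 applies to eligible patients, whereas the endpoint counts eligible patients approached. If some eligible patients are never approached, the rate among those approached would be higher than 50%. The 0.9997 is therefore illustrative.
- The amendment log explains 40 against 55: 55 are to be enrolled so that about 40 have pre-post data. That accounts for the two numbers, but Section 9.2 still uses a count of evaluable cases as a count of recruits. Since enrolling 55 means approaching at least 55, the printed limit has meaning only if read at the 40th enrollment.

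**Conclusion.** The concern holds. On Section 9.2's own inputs the probability is 0.978, not below 0.05. The reading built on it conflicts with the protocol's criterion of at least 60% for every result from 55 to 66 approached with 40 enrolled. That conflict has probability 0.49 at a true rate of 60%, 0.71 at 65% and 0.65 at 70%, so it falls where a successful study is likely to land. The calculation assumes independent enrollment decisions at a constant rate, as the plan's negative binomial model does, and needs no outside figure. The error is confined to the justification and feasibility reading in Section 9.2; the Section 9.4.2 test is unaffected. It should be fixed before the limit is applied or reported.

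**What to change.** Delete the probability and its interpretation from Section 9.2, or recompute them and name the number enrolled to which they apply.

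If a flag for possible infeasibility is kept, use 79 or more approached for 40 enrolled, or 106 or more for 55 enrolled, and state two limitations:
- Reaching the limit is borderline evidence of enrollment below 60%. The fixed-sample exact test there is not significant, and its confidence interval includes 60%.
- Staying under the limit does not show enrollment of at least 60%. With 67 to 78 approached for 40 (59.7% to 51.3%), or 92 to 105 for 55 (59.8% to 52.4%), the observed rate misses the criterion without being flagged. A true 50% rate is flagged only 55% or 65% of the time.

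Add a cross-reference saying that the 60% criterion and the Section 9.4.2 test govern the primary conclusion. Because the two can differ, as at 40 of 60, say what each one decides.

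The cost is wording in Section 9.2 and one cross-reference, with no extra patients or data. The operating characteristic stated will look less favourable than the one now printed.

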#### Primary Objectives

1. To refine the Pathways intervention and study protocol based on acceptability feedback from an open pilot study (i.e., fully implement the intervention) with patient exit interviews ( $n = 6$ ). We will use feedback on the acceptability of session content, length, and delivery, and review intervention session recordings to refine the intervention. If necessary, we will refine the procedures for enrollment and retention.
2. To determine Pathways intervention feasibility in a single-arm pilot study ( $n = 55$  Pathways). Feasibility will be defined by enrollment ( $\geq 60\%$ ); primary feasibility outcome, retention ( $\geq 70\%$ ), adherence ( $\geq 70\%$  of patients completing 3 of 5 sessions), and mean acceptability ratings (scores of  $\geq 7$  out of 10 on intervention relevance, helpfulness, and convenience).

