#### PRIMARY OBJECTIVES OF PHASE II

1. To determine Pathways intervention feasibility (Phase II;  $n = 55$  Pathways). Feasibility will be defined by enrollment ( $\ge 60\%$  primary feasibility outcome), retention ( $\ge 70\%$ ), adherence ( $\ge 70\%$  of patients completing 3 of 5 sessions), and mean acceptability ratings (scores of  $\ge 7$  out of 10 on intervention relevance, helpfulness, and convenience).
2. To assess preliminary data on intermediate and outcome variables and clinical utility in the single-arm pilot of Pathways (Phase II). We will assess pre (baseline) to post (~8 weeks after baseline) changes in intermediate (e.g., hope) and outcome (primary: activity and role function) variables related to a future efficacy trial. We will also describe the number of referrals to supportive services made based on the Pathways intervention.

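### Section 9.2 misstates the retention tail probability (0.074, not below 0.05) and sets its only retention warning limit at an unexplained 60%, out of 40, against a criterion of at least 70% and a sample of 55

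*Combined protocol and SAP*

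**What the plan says.** The Synopsis (1.1, Primary Objectives), Section 3 (Primary Objectives of Phase II) and the opening of the Phase II paragraph in 9.2 all require retention of at least 70%.

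Section 9.2 then gives a separate warning limit. It takes 40 patients and says that "if the true probability of retention is 60% we expect at least 19 patients will be retained". In parentheses it puts the probability of 19 or fewer "retained given true retention probability of 60% is" below 0.05. It concludes: "so if more than 21 patients are not retained, an efficacy study may not be feasible".

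Four other places bear on how to read this.

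- The same paragraph opens with "The target sample size of 40 evaluable cases for Phase II".
- The enrollment sentence just before uses enrollment's own 60% criterion as its reference: with "55 patients to enroll 40, it is unlikely the true probability of enrollment is 60% or greater". It is cited here only for that choice of rate; its arithmetic is not examined.
- The adherence sentence just after also uses a value below its 70% criterion, but names it: "if we assume a null hypothesis adherence proportion of 0.50".
- Section 9.3 gives 55 as the Phase II sample for feasibility analyses. Section 9.4.2, repeated in the separate Analysis Plan, defines retention as the percentage completing the baseline and post-treatment questionnaires. It names a test value for enrollment only.

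**The concern.** Three things do not fit together. The printed probability cannot be reproduced. The reference rate is ten points below the retention criterion, with no label or reason. The limit is counted out of 40, while the feasibility sample is 55.

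At stake is how a retention result will be read. Section 9.4.1 and the Analysis Plan promise tests of feasibility rates against hypothesized values. For retention a reader finds two candidates, 70% and 60%, and two possible denominators. The expected yield in the amendment history, 40 evaluable cases from 55 enrolled (40/55 = 72.7%), lies close to the 70% criterion, so a result that has to be argued over is quite possible.

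**Working it through.** **Inputs.** From 9.2: n = 40, reference rate 0.60, stated tail below 0.05 for 19 or fewer retained, warning if more than 21 are not retained. From 1.1, 3 and 9.2: criterion at least 70%. From 9.3: Phase II sample 55. From the version 7 entry in Section 13: 55 enrolled expected to yield 40 evaluable.

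**Formula.** With X retained out of n and true rate p, P(X ≤ k) = Σ C(n,i) pⁱ (1−p)ⁿ⁻ⁱ for i = 0 to k.

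**Step 1: the plan's own figure.** For n = 40 and p = 0.60, P(X ≤ 18) = 0.0392 and P(X = 19) = 0.0352. So P(X ≤ 19) = 0.0392 + 0.0352 = 0.0744, which is not below 0.05. Other forms do not rescue it: normal approximation 0.053, with continuity correction 0.073, mid-p 0.057, doubled tail 0.149.

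**Step 2: the operative rule.** More than 21 of 40 not retained means 22 or more lost, so 40 − 22 = 18 or fewer retained, with probability 0.039. The expectation of at least 19 retained agrees with this. Only the parenthesis is wrong; it should read 18 or fewer.

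**Step 3: the limit against the criterion.** 0.70 × 40 = 28, so 27 or fewer of 40 misses the criterion. The limit is reached only at 18 or fewer (45%). Results of 19 to 27 of 40 (47.5% to 67.5%) miss the criterion without reaching the limit.

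**Step 4: limits on 55 patients.**
- Reference 70%: P(X ≤ 32) = 0.042 and P(X ≤ 33) = 0.073, so the one-sided limit is 32 or fewer, that is, 23 or more not retained. By a two-sided exact test it is 31 or fewer (p = 0.038; 32 gives p = 0.076).
- Reference 60%: P(X ≤ 26) = 0.038 and P(X ≤ 27) = 0.066, so the one-sided limit is 26 or fewer.
- Observed criterion: 0.70 × 55 = 38.5, so 39 or more meets it.

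**Step 5: how often each one-sided limit is reached.**

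| True retention | 18 or fewer of 40 (as in 9.2) | 26 or fewer of 55 (60%) | 32 or fewer of 55 (70%) |
|---|---|---|---|
| 50% | 32% | 39% | 91% |
| 55% | 13% | 15% | 73% |
| 60% | 4% | 4% | 44% |
| 65% | 0.7% | 0.5% | 18% |
| 70% | 0.1% | <0.1% | 4% |

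The reference rate drives nearly all of the difference. Moving from 40 to 55 at a fixed 60% changes little. At the expected 72.7%, the 70% limit would be reached about 1.4% of the time.

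**The case against.** The strongest reply is that nothing goes wrong in practice. Feasibility is defined by observed retention of at least 70%, and a result below that fails whatever 9.2 adds. The planned 95% confidence intervals would also show the shortfall: 19 of 40 has an exact upper limit of 63.9%, which excludes 70%. The limit in 9.2 is offered as a basic calculation and ends only in a statement that a later trial may not be feasible. The off-by-one moves nothing, and retention is not the primary endpoint. All of this stands, and it limits the size of the point.

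A reader might go further and infer that 9.2 would declare 47.5% retention feasible. It does not; it is silent between 19 and 27 of 40.

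A reader might also infer that retention is computed among patients who are retained by definition, because the amendment history explains evaluable cases as those with pre-post data. The text does not support that. The retention sentence speaks simply of 40 patients, and the enrollment sentences before it treat 40 as the number recruited. The amendment history also shows that 40 was the Phase II sample size before it rose to 55. An enrolled count that was not updated is the likelier reading, though still an inference. For the same reason, the count of 21 should not be applied to 55 patients; the plan sets it out of 40.

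Finally, 60% may be a deliberate lower limit, as 0.50 appears to be for adherence. The documents do not rule this out, but they do not say it.

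**Conclusion.** The point holds as a text correction worth making. One printed probability is wrong (0.074 against a stated value below 0.05), without consequence for the limit. The only numerical warning limit for retention rests on an unexplained 60% against a criterion of at least 70%, and would miss a true rate of 50% about 68% of the time (100% − 32%). Its denominator of 40 is not reconciled with the sample of 55. The finding is a misaligned limit, not an opposite verdict, and whether 60% is a slip or a choice cannot be settled from the documents.

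The figures assume independent patients with a common retention rate and, for the restated limits, exactly 55 in the denominator. Section 7.2 allows replacement of consented patients who receive no intervention, so the actual number may differ.

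**What to change.** First settle what 60% is meant to be, then rewrite the retention sentence in 9.2 on the enrolled Phase II patients (planned 55, recomputed for the actual number).

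- If the reference is the criterion: *If true retention is 70%, the one-sided probability that 32 or fewer of 55 are retained is 0.042; if 23 or more are not retained, an efficacy study may not be feasible.*
- If 60% is a deliberate lower limit, label it so: 26 or fewer of 55 retained, one-sided P = 0.038.
- If 40 is kept, give the reason and change 19 or fewer to 18 or fewer in the parenthesis.

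In every case keep the observed criterion of at least 70% (39 or more of 55). Even the 70% limit leaves 33 to 38 of 55 (60.0% to 69.1%) missing the criterion without reaching the limit. State the retention test value and its sidedness in 9.4.2 and in its copy in the Analysis Plan, and name the confidence interval method. The method can matter: 22 of 40 has an upper limit of 70.7% by Clopper-Pearson and 69.3% by Wilson.

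The cost is a few lines of text; sample size and the primary enrollment analysis do not change. The drawback is timing. A 70% limit is stricter, and attrition was already known at the amendment of 11/10/2021, so the change should be dated and the retention data already seen should be disclosed.

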## 9.3 POPULATIONS FOR ANALYSES

The sample from phase I ( $n = 6$ ) will be used to refine procedures and the intervention protocol. The sample from phase II ( $n = 55$ ) will be used to analyze feasibility and acceptability data and describe pre-post changes in patient-reported outcomes.

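### Does the 80% power quoted for adherence (0.72 against a null of 0.50) misstate the chance of meeting the 70% adherence criterion?

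*Combined protocol and SAP*

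**What the plan says.** The Phase II objectives in Section 3 define feasibility through several measures. Enrollment of at least 60% is primary. Adherence is met when at least 70% "of patients completing 3 of 5 sessions" is observed. Section 9.2 repeats the 70% threshold and introduces its figures with "Here we present some basic power calculations for the above 3 outcomes". For adherence it gives one figure, 80% power at a two-sided 5% level, "to detect an adherence proportion of 0.72 if we assume a null hypothesis adherence proportion of 0.50". That section works from 40 evaluable cases. Section 9.3 says the Phase II sample of 55 "will be used to analyze feasibility and acceptability data and describe pre-post changes in patient-reported outcomes".

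For the analysis, Section 9.4.1 and the separate Analysis Plan call for 95% confidence intervals on each feasibility measure and for "tests of binomial proportions to compare rates of feasibility to hypothesized values". Section 9.4.2 names a test value only for the primary measure: "A one-sample binomial test will be used to compare the observed enrollment percentage to 60" per cent. It defines adherence as at least 3 of 5 sessions in 10 weeks and gives no test value for it.

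**The concern.** The power statement uses a null of 0.50 with no explanation, for an outcome whose threshold is 70%. The alternative, 0.72, lies just above that threshold, so a quick reader could take 80% as the chance of showing feasible adherence when the true rate is 0.72. That chance is lower.

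There is also a possible conflict at the analysis stage. The plan speaks of hypothesized values and names none for adherence, and 0.50 is the only adherence null printed anywhere. If the test were run against 0.50, adherence in the high 60s could be reported as statistically significant although the protocol's own criterion had been missed. At stake would be a favourable adherence statement carried into the planning of an efficacy trial.

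**Working it through.** **Inputs.** Null 0.50, alternative 0.72, two-sided alpha 0.05 and n = 40 (Section 9.2); n = 55 (Section 9.3); criterion of at least 70% (Sections 3 and 9.2). The documents do not say whether the adherence denominator is 40 or 55, so both are shown. X is the number of adherent patients, binomial(n, p).

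**1. The plan's own figure.** The upper rejection boundary is the smallest r with P(X ≥ r | 0.50) ≤ 0.025.

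- n = 40: P(X ≥ 27) = 0.0192 and P(X ≥ 26) = 0.0403, so r = 27 (67.5%). Power = P(X ≥ 27 | 0.72) = 0.794. The stated 80% reproduces.
- n = 55: P(X ≥ 36) = 0.0150 and P(X ≥ 35) = 0.0290, so r = 36 (65.5%). Power = P(X ≥ 36 | 0.72) = 0.889.

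**2. Chance of meeting the criterion.** The smallest passing count is 0.70 × 40 = 28, or 0.70 × 55 = 38.5, rounded up to 39 (70.9%).

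| True adherence | P(X ≥ 28), n = 40 | P(X ≥ 39), n = 55 |
|---|---|---|
| 0.60 | 0.129 | 0.063 |
| 0.65 | 0.314 | 0.220 |
| 0.70 | 0.577 | 0.508 |
| 0.72 | 0.684 | 0.637 |
| 0.75 | 0.821 | 0.806 |
| 0.80 | 0.957 | 0.963 |

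At 0.72 the pass probability is 0.794 − 0.684 = 0.110 below the power of the 0.50 test at n = 40, and 0.889 − 0.637 = 0.252 below it at n = 55. Part of the gap at 55 comes from rounding 38.5 up to 39. With a true rate two points above the cut-off, any rule based on the observed rate passes only moderately often.

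**3. Results that reject 0.50 but miss 70%.** At n = 40 this is the single count 27. At n = 55 it is 36 to 38 (65.5% to 69.1%).

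| True adherence | n = 40 (X = 27) | n = 55 (X = 36 to 38) |
|---|---|---|
| 0.60 | 0.083 | 0.184 |
| 0.65 | 0.127 | 0.314 |
| 0.72 | 0.110 | 0.253 |

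These probabilities matter only if a test against 0.50 is run and read as the feasibility decision.

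**4. What the planned interval would show.** Exact 95% limits are 50.9% to 81.4% for 27/40 and 53.5% to 83.4% for 28/40. They are 51.4% to 77.8% for 36/55 and 55.2% to 80.9% for 38/55. Each result in the zone of conflict would be reported as an observed rate below 70% with a wide interval that contains 70%.

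**5. Is 0.50 the planned test value?** It appears only in Section 9.2. For enrollment, Section 9.1 hypothesizes at least 60% and Section 9.4.2 tests against that same 60%, which is also the feasibility criterion. By the same usage the hypothesized value for adherence would be 70%. Nothing in the analysis sections points to 0.50.

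**The case for a change.** The strongest case for a change is this. Section 9.2 offers its figures as power calculations for outcomes that it has just defined by thresholds, and the adherence figure is the only operating characteristic given for that outcome. Nothing labels 0.50 as an unacceptable rate, and Section 9.4.2 leaves the adherence test value blank, so an analyst looking for one finds only 0.50. With 55 patients the zone of conflict covers three counts and has probability 0.31 at a true rate of 65%. The interval alone does not settle the matter, since at 38/55 it excludes 50% and includes 70%. A sentence would cost almost nothing.

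Part of this stands. The null is unlabelled, no operating characteristic is given for the 70% rule, and the adherence test value is unnamed.

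The step from there to a wrong conclusion does not stand. Section 9.2 prints its null, alternative, alpha and sidedness in full, so the figure claims nothing beyond itself, and power against a low null is an ordinary convention. The interval need not settle feasibility, because the objectives already do so through the observed rate. No section makes a p-value against 0.50 a feasibility rule. Testing for superiority over 70% would not help either: it would need 34/40 or 46/55 and would reject upward with probability only 0.043 or 0.033 at a true rate of 0.72.

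**Conclusion.** No change is needed. The 80% is arithmetically sound at n = 40 (0.794 exact). It differs from the chance of passing the 70% criterion at a true rate of 0.72 (0.68 at n = 40, 0.64 at n = 55), but the plan does not equate the two.

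Followed as written, the plan gives a sound answer on adherence: the observed rate is set against 70% and reported with its 95% interval. A result of 27/40, or 36 to 38 of 55, fails that criterion regardless of any test against 0.50. Labelling the null or tabulating pass probabilities would help a reader but would change neither the sample size, the data collected nor any conclusion. Adherence is also not the primary feasibility measure; enrollment is.

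This rests on two readings: that the 70% in the objectives decides adherence feasibility, as the text there says, and that 0.50 served only for sample-size planning, which fits its absence from every analysis section. The choice of denominator, 40 or 55, moves the figures but not the conclusion.
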